10.7.3 Electrocardiograms

All ECG results will be listed by subject.

10.7.4 Vital Signs

A subject listing, using the SAS, will be provided for all vital signs results. Results meeting PCI criteria (see [Table 8](#)) will be flagged in the listing.

Observed values of SBP, DBP, pulse rate, respiratory rate, temperature, and body weight at baseline and at selected postbaseline time points, and change from baseline in these parameters at each postbaseline time point, will be summarized descriptively by treatment group.

10.7.5 Physical Examinations

Any clinically significant findings during physical examinations are to be reported as medical history or AEs, depending on timing. No separate listing will be provided for physical examination results.

10.8 Pharmacokinetics

AVTX-002 plasma concentrations will be listed by subject (using the PK Analysis Set), and will be summarized by visit and treatment group, for the PK Analysis Set.

10.9 Pharmacodynamics

Results from sputum soluble LIGHT levels and gene expression, inflammatory biomarkers, and immunophenotyping of immune cell subsets are reported separately (as applicable) and will not form part of the statistical analysis described in this SAP.

Results from serum soluble LIGHT levels will be listed by subject in a subject listing, and descriptive statistics for actual as well as change from baseline values will be presented by treatment group and time point, using the FAS.

10.10 Immunogenicity

For the immunogenicity variables (ie, ADA), results will be listed by subject in a subject listing, and descriptive statistics for actual as well as change from baseline values will be presented by treatment group and time point, using the SAS.

12 APPENDICES

Appendix 1. Schedule of Assessments and Procedures

Note: refer to [Section 8](#) for changes to numbering of assessment day, for purposes of reporting of study results. The assessment day as presented in [Table 2](#) below, reflects the numbering as presented in the study protocol.

Table 2. Schedule of Assessments (as per V4 study protocol)

Procedure	Screening	30day Runin	Baseline	Doubleblind Treatment Period							
				Visit 1	Visit 1a	Visit 2	Visit 3	Visit 4	Visit 5	Visit 6	Visit 7
Visit											
Assessment Week	-4				0	1	2	4	6	8	12
Assessment Day	Appr -37 ¹	-30	-7	0	7	14	28	42	No later than 56 ³		
				-1							
Visit Window ⁴	NA			-2 days	+3 days ⁵	±1 day	±1 day	±3 days	±3 days	±3 days	±3 days
Phone visit				X ⁶							
Informed consent	X										
Inclusion/exclusion review	X				X						
Demographics	X										
Medical history	X										
Prior medications	X										
Randomization											
Concomitant medications	X										
Adverse events	X ⁸	X	X	X	X	X	X	X	X	X	X
Vital signs	X			X ⁷	X	X ⁷	X	X ⁷	X	X	X
Physical examination	X			X	X	X	X	X	X	X	X
12-lead ECG	X			X	X	X	X	X	X	X	X
FEV ₁	X			X	X	X	X	X	X	X	X
FeNO	X	X	X	X	X	X	X	X	X	X	X
Peak Flow Test (daily) ^{9,17}	X	X	X	X	X	X	X	X	X	X	X
ACQ	X	X	X	X	X	X	X	X	X	X	X
AQLQ(S)+12	X	X	X	X	X	X	X	X	X	X	X
ASD (2x daily) ¹⁷	X	X	X	X	X	X	X	X	X	X	X
Record SABA use (2x daily) ¹⁸	X	X	X	X	X	X	X	X	X	X	X
EQ-5D-5L	X	X	X	X	X	X	X	X	X	X	X

Statistical Analysis Plan: AVTX-002-NEA-201
AVTX-002

Avalo Therapeutics, Inc.
Final 4.0, 02 Jun 2023

Procedure	Screening		30day Runin Period		Doubleblind Treatment Period											
	Visit	Visit 1	Visit	Visit 1a	Visit 2	Visit 3	Visit 4	Visit 5	Visit 6	Visit 7	Visit 8	Visit 9/ ET ²				
Assessment Week	-4				0	1	2	4	6	8	12	14				
Assessment Day	Appr -37 ¹	-30	-7	0	7	14	28	42	No later than 56 ³	84	98					
Visit Window ⁴	NA		-2 days	+3 days ⁵	±1 day	±1 day	±3 days	±3 days	-3 days	±3 days	±3 days					
PGI-C/S			X		X		X		X		X					
CGI-I/S			X		X		X		X		X					
ADA ¹⁰			X		X		X		X		X					
Serum: soluble LIGHT			X		X		X		X		X					
Inflammatory proteins		X		X		X		X		X						
Immunophenotyping of circulating immune cells			X		X		X		X		X					
Sputum: soluble LIGHT and gene expression ¹¹			X								X					
Plasma AVTX-002 level			X	X	X	X	X	X	X	X	X					
Clinical laboratory tests (hematology, clinical chemistries)		X		X		X		X		X		X ¹⁶				
Urinalysis	X		X		X		X		X		X					
Serum pregnancy test ¹²		X		X		X		X		X		X				
Urine pregnancy test ¹²		X		X		X		X		X		X				
Study drug administration (onsite) ^{13,14,15}		X		X		X		X		X		X				
Salmeterol/Fluticasone runin		X		X		X		X		X		X				
Discontinue salmeterol																
Taper/discontinue fluticasone			X		X		X		X		X					

ACQ = Asthma Control Questionnaire; ADA = anti-drug antibody; AE = adverse event; AQLQ(S)+12 = Standardized Asthma Quality of Life Questionnaire for 12 to 70 years; ASD = Asthma Symptom Diary; CGI-I/S = Clinician Global Impression of Improvement/Severity; ECG = electrocardiogram; EQ-5D-5L = European Quality of Life – 5 dimension 5 level questionnaire; ET = early termination; FeNO = fractional exhaled nitric oxide; FEV₁ = forced expiratory volume in 1 second; GLIGHT = Lympphotoxin-like, exhibits Inducible expression, and competes with Herpes Virus Glycoprotein D for Herpesvirus Entry Mediator, a receptor expressed by T lymphocytes; PGI-C/S = Patient Global Impression of Change/Severity; SABA = short-acting beta agonist

- Documentation of eligibility on all inclusion and exclusion criteria is required before a subject can enter the study 30-day run-in period prior to Visit 2 (randomization) when the subject is switched to stand alone salmeterol and fluticasone. Confirmation of eligibility should take place within a reasonable amount of time after the Screening Visit. If confirmation of eligibility is not available within 14 days from the date of screening, the study sponsor should provide approval for the subject to continue.
- If a subject discontinues from the study/study drug, the Visit 9/ET procedures will be performed 4 weeks post last dose (±3 days).
- A subject must be dosed with the Visit 7 (Week 8) dose no later than Day 56.

Procedure	Screening		30day Runin		Baseline		Doubleblind Treatment Period						
	Visit	Visit 1	Visit	Visit 2	Visit 3	Visit 4	Visit 5	Visit 6	Visit 7	Visit 8	Visit 9/ ET ²		
Assessment Week	-4		1a		0	1	2	4	6	8	12	14	
Assessment Day	Appr -37 ¹		-30		-7	0	7	14	28	42	No later than 56 ³	84	98
Visit Window ⁴	NA		-2 days	+3 days ⁵	±1 day	±1 day	±3 days	±3 days	-3 days	±3 days	±3 days		
													-1
4.													
5.													
6.													
7.													
8.													
9.													
10.													
11.													
12.													
13.													
14.													
15.													
16.													
17.													
18.													

Appendix 2. Imputation of Partial Dates

Table 3. Imputation Rules for Partial Dates – Adverse Events

Parameter	Missing	Additional Condition	Imputation
Start Date	D only	M and Y are prior to first study drug dose	First day of indicated month
		M and Y is same as first study drug dose	Date of first study drug dose
		M and Y are after first study drug dose	First day of indicated month
	M and D	Y is prior to first study drug dose	01 Jan of indicated year
		Y is same as first study drug dose	Date of first study drug dose
		Y is after first study drug dose	01 Jan of indicated year
	M, D, and Y	---	assumed to be TEAE
	End Date	M and Y are prior to last study drug dose	Last day of indicated month
		M and Y is same as last study drug dose	Date of last observation if within indicated M and Y; if date of last observation extends after indicated M and Y, then use last day of indicated month
		M and Y are after last study drug dose	First day of indicated month
M and D	Y is prior to last study drug dose	31 Dec of indicated year	
		Date of last observation if within indicated Y; if date of last observation extends after indicated Y, then use 31 Dec of indicated year	
	Y is same as last study drug dose	01 Jan of indicated year	

	Y is after last study drug dose	TEAE is ongoing	
M, D, and Y	---	Estimated end date is before a complete or imputed AE start date	Last day of the month of AE start date

AE = adverse event; D = day; M = month; TEAE = treatmentemergent adverse event; Y= year

Note: The imputation of end date must be later than start date

Table 4. Imputation Rules for Partial Dates – Prior and Concomitant Medications and Procedures

Parameter	Missing	Additional Condition	Imputation
Start Date	D only	M and Y same as M and Y of first study drug dosing	Date of first study drug dose
		M and/or Y not the same as M and Y of first study drug dosing	First day of indicated month
	M and D	Y same as Y of first study drug dosing	Date of first study drug dose
		Y not the same as Y of first study drug dosing	01 Jan of indicated year
	M, D, and Y	---	Date of first study drug dose
		End date < date of first study drug dose	End date
	End Date	M and Y same as M and Y of last study drug dosing	Date of last study drug dose
		M and/or Y not the same as M and Y of last study drug dosing	Last day of indicated month
M and D	Y same as Y of last study drug dosing	Date of last study drug dose	
		Y not the same as Y of last study drug dosing	31 Dec of indicated year
	M, D, and Y	---	Date of last study drug dose

D = day; M = month; Y= year

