10.7.1 Adverse Events

All AEs are collected from the time that the informed consent is signed until the end of study.

The definition for an AE to be considered treatmentemergent is as follows:

- If AE start time is recorded: an AE will be considered treatmentemergent if it occurs on or after the time of first dose of investigational product and within 28 days after a subject's last dose of investigational product.
- If AE start time is not recorded: an AE will be considered treatmentemergent if it occurs on or after the date of first dose of investigational product and within 28 days after a subject's last dose of investigational product.

Additionally, an AE that occurred prior to the date of first study drug dosing and increased in severity after start of first dosing and within 28 days of a subject's last dose of investigational product will also be considered treatment-emergent. An AE that occurred prior to first study drug dose and then again after first study drug dose at the same severity is NOT considered treatment-emergent.

AE verbatim terms will be coded to a SOC and PT using MedDRA, version 24, 01 Sep 2021.

For incidence of AEs by treatment group, SOC and PT, a subject will be counted only once per SOC and PT.

For AE incidence presented as the number and percentage of subjects with a specific AE, if there is more than one occurrence of an event, the event with the worst severity or the highest rated causality category will be summarized.

Summaries of AEs by SOC and PT will be sorted alphabetically for SOC, then by descending order of frequency of PT (for AVTX-002) within each SOC (then alphabetically for ties).

Summaries of AEs by PT will be sorted by descending order of frequency of PT (for AVTX-002), then alphabetically for ties.

Missing assessments of seriousness, intensity and relationship to study drug that have been queried and remain missing, will be treated 'worst case' for presentation filtering purposes as follows:

- Missing seriousness assessment: AE will be regarded as serious.
- Missing relationship to study drug: AE will be regarded probably related to study drug, except when start date is prior to first dose of study drug (in which case the AE will be regarded not related to study drug).
- Missing intensity assessment:
 - If subject has died, AE will be regarded Grade 5 intensity.
 - If subject has not died but subject had intervention indicated for the AE, AE will be regarded Grade 4 intensity.

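### SAP Table 3 can date an adverse event that ended before dosing to the day of first dose, so it counts as treatment-emergent

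*SAP*

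**What the plan says.** SAP 9.3 states that the partial-date rules exist so that AEs can be classified, and that listings keep the dates as collected. The rules are in SAP Appendix 2, Table 3. Its Start Date block covers three patterns:

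- Day missing: under the condition "M and Y is same as first study drug dose", the start becomes the date of first dose.
- Month and day missing: under the condition "Y is same as first study drug dose", the same.
- Everything missing: "assumed to be TEAE".

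None of these rows refers to the AE end date. Table 3 has two start/end consistency provisions. One row applies when "Estimated end date is before a complete or imputed AE start date" and resets the end to the last day of the start month. The note reads "The imputation of end date must be later than start date". Both act on the end date only.

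SAP 10.7.1 defines treatment emergence from the start. Where no start time was recorded, "an AE will be considered treatmentemergent if it occurs on or after the date of first dose of investigational product", up to 28 days after the last dose. For a causality that is still missing after query, the same section says "AE will be regarded probably related to study drug, except when start date is prior to first dose of study drug".

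Table 4, which does the same job for medications and procedures, has a row "End date < date of first study drug dose" that sets the start to the end date. Table 3 has no counterpart.

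**The concern.** AEs are collected from informed consent (protocol 11.1.1, SAP 10.7.1), so the database includes the 30-day run-in, when subjects are switched to stand-alone salmeterol and fluticasone and have had no study drug. An AE that began and ended in that period cannot be treatment-emergent. If its start date is incomplete, Table 3 can still place it on the first-dose date and so in the TEAE tables, including those by grade and seriousness.

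There is a second step. The exemption from the worst-case causality rule depends on the start being before first dose. Once the start has been moved to first dose, the exemption is lost. If causality also stays missing after query, the AE is regarded as probably related.

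Imputing to first dose is sound when the end date is unknown, ongoing, or on or after first dose. The fault is limited to cases where the recorded end already settles the question.

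**Working it through.** The plan states no figure to reproduce. The check applies the rules literally to dated examples.

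**Rules used.** F = first-dose date, L = last-dose date, E = AE end date, S* = imputed start.

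- S* = F if the known start month and year, or the year alone, match F (Table 3).
- An AE with a fully missing start is a TEAE (Table 3).
- Otherwise, an AE is a TEAE if F ≤ S* ≤ L + 28 days (SAP 10.7.1, no start time recorded).

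**Basic case.** Start --/Mar/2022, E = 05 Mar 2022, F = 10 Mar 2022. The month and year match, so S* = 10 Mar. E − S* = −5 days: the event ends five days before it starts. S* = F satisfies the definition, so it is a TEAE.

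**Each missing pattern.** F = 20 Sep 2022 and L = F + 56 days = 15 Nov 2022, so the window closes on 13 Dec 2022.

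| Case | Recorded start | Recorded end | S* | TEAE as written | TEAE with an end-before-first-dose check |
|---|---|---|---|---|---|
| a | Sep 2022, day missing | 10 Sep 2022 | 20 Sep 2022 | yes | no |
| b | 2022 only | 10 Sep 2022 | 20 Sep 2022 | yes | no |
| c | 2022 only | Aug 2022, day missing | 20 Sep 2022 | yes | no |
| d | fully missing | 10 Sep 2022 | none | yes | no |
| e | Aug 2022, day missing | 10 Sep 2022 | 01 Aug 2022 | no | no |

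All of these AEs were over before dosing, and four of the five are misclassified. Case e is right because its known start month precedes the month of first dose.

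In case c the end is first estimated as 31 Aug 2022. That is before S*, so the consistency row moves it to 30 Sep 2022, and the event then appears to lie wholly after first dose. The End Date block of Table 3 is not cleanly aligned in the copy at hand, so this detail depends on how that row is read. The TEAE result does not.

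**How often the first-dose rows apply before dosing.** Assume first-dose dates are spread evenly over the calendar year. Share = pre-dose days in the same month (or year) as F, divided by all pre-dose days.

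- 30-day pre-dose period: 0.49 same month, 0.96 same year.
- 37-day pre-dose period (the approximate screening day in the assessment schedule): 0.40 same month, 0.95 same year.

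These shares show how often a pre-dose day falls where the first-dose rows apply. They do not estimate misclassified AEs: an AE is provably wrong only if its start is also incomplete and its end is known to precede first dose.

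**Size per subject.** With 40 subjects per arm (SAP 6.1.1), 1/40 = 2.5 percentage points for one added subject in one row. SAP 10.7.1 counts a subject once per system organ class and preferred term, so a subject already in a row adds nothing to it.

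**The case against.** The strongest reply is that this is a rare edge case in a deliberately conservative scheme. SAP 10.7.1 already takes the worst case for missing seriousness, causality and intensity. Several steps narrow the pool: protocol 11.1.1 sends most clinically significant screening observations to medical history, and protocol 13.3.2 requires sites to resolve data queries. The causality step needs a further unresolved gap, and protocol Table 3 gives investigators a not-related category that expressly covers events without exposure. Safety analyses are descriptive, and the all-AE listing shows dates as collected, so a careful reader would see the pre-dose end.

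All of that limits the consequence, and it stands. It does not defend the rule. A worst-case convention fills in what is unknown; here the recorded end rules out treatment emergence. SAP 10.7.1 also says that an AE present before first dose and recurring afterwards at the same severity is not treatment-emergent. An event that ended before dosing and did not recur has a weaker claim still.

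A reader might infer that Table 4 already applies the needed guard to every missing pattern. It does not clearly do so: as the table reads, the guard stands only beside the fully missing start, and the other Table 4 rows send matching starts to first dose just as Table 3 does. Table 4 shows that the SAP recognises the problem for medications; it is not a complete model to copy.

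**Conclusion.** The point holds: Table 3 is wrong as written for AEs with an incomplete start that matches the month and year (or year alone) of first dose, or with no start at all, and whose end is known to precede first dose. Severity is minor.

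The number of such AEs is not given in the documents and is probably small. Because the events precede randomized treatment, no direction between arms is expected, and the efficacy analyses do not use these dates. The largest effect per subject is 2.5 points in a TEAE row for an arm of 40, and nothing if the subject is already in that row.

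A reader might go further and take the 40% to 49% and 95% to 96% shares as misclassification rates, or conclude that run-in AEs in general become TEAEs. Neither follows. AEs with complete start dates, or with a known start month before the month of first dose, are classified correctly. The shares rest on an assumed even spread of first-dose dates and mostly describe ordinary, defensible imputation.

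**What to change.** Add a condition to the Start Date block of Table 3, applied before the other start rows and before any adjustment of the end date:

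- If the AE end date is complete and before first dose, or is partial and its latest possible date is before first dose, classify the AE as not treatment-emergent.
- Impute its start no later than that end: the first day of the known start month if only the day is missing; otherwise the end date, or its latest possible date if partial. If only the year is known and it precedes the year of first dose, the existing 01 January rule already works and can stay.
- Keep first-dose imputation when the end is unknown, ongoing, or possibly on or after first dose.

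The order matters, because the existing consistency row would otherwise move a partial pre-dose end past first dose. The pre-dose causality exemption then works without further change. The cost is a short addition to one SAP table and a small change to the AE derivation program, with no new data to collect.

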An asthma exacerbation requiring the use of systemic corticosteroids (tablets, suspension, or injection) for ≥ 3 days **	Prior and Concomitant Medications page of eCRF, coded appropriately so that systemic corticosteroids can be identified	Not applicable
A hospitalization or emergency room visit because of an asthma exacerbation	Asthma exacerbation reported as SAE; in case SAE was not reported (ie, in case asthma exacerbation required only emergency room visit which consequently is not reported as SAE), the Investigator assessment in the eCRF of occurrence of an asthma related event is to be utilized as the source data	Not applicable

ICS = inhaled corticosteroid; SABA = short-acting beta agonist

- * This criterion may be met via 2 consecutive calendar days of assessments (ie, morning and evening diary entries for calendar date 1) plus morning and evening diary entries for the calendar date 2) or over a span of 3 consecutive calendar days (ie, evening diary entry for calendar date 1 and morning diary entry for calendar date 2 plus evening diary entry for calendar date 2 and morning diary entry for calendar date 3).
- ** In the case which use of systemic corticosteroids being administered for an asthma exacerbation is ongoing at the end of the study, the duration will be considered to be ≥ 3 days – as in clinical practice corticosteroid prescription including tapering usually last more than 3 days – and therefore the subject will be considered to have met this criterion for an asthma related event.
- ** Subjects being administered systemic corticosteroids for ≥ 3 days for a nonasthma event, will be considered to have met this criterion for an asthma related event, provided they have corresponding signs and symptoms of an asthma exacerbation. Also, subjects being administered a single dose of a longterm acting systemic corticosteroid (eg, dexamethasone) with a dose equivalent to a treatment of ≥ 3 days with other short to midterm systemic corticosteroids will be considered to have met this criterion for an asthma related event. Such cases will be confirmed by the sponsor as having met the criterion for an asthma related event or not.

In addition, an Investigator assessment of the occurrence of an asthma related event is recorded in the eCRF at each visit during the course of the study.

Time to first asthma related event will be measured in days as follows:

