9.3 Handling of Partial Dates

Rules for imputation of missing or partial dates to enable background calculation/classification of AEs and prior/concomitant medication/procedures are presented in [Appendix 2](#).

Listings will display the dates as collected on the eCRF.

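### SAP Table 4 can set a medication's end date before its start date, and the SAP gives no other rule for the 3-day steroid criterion when a completed course has an incomplete stop date

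*SAP*

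**What the plan says.** SAP Appendix 2, Table 4 (medications and procedures), End Date rows:

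- Day missing, condition "M and Y same as M and Y of last study drug dosing": the end becomes "Date of last study drug dose".
- Day missing, condition "M and/or Y not the same as M and Y of last study drug dosing": the end becomes the last day of the recorded month.
- Month and day missing, condition "Y same as Y of last study drug dosing": the end becomes the last dose date. In a different year it becomes 31 December of the recorded year.
- Day, month and year all missing: the end becomes the last dose date, unconditionally.

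No End Date row refers to the start date. Table 4 protects date order only for a fully missing start date.

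Table 3 (adverse events), in the same appendix, does protect it. It falls back to the last day of the start month when the estimated end precedes the start, and its footnote reads "Note: The imputation of end date must be later than start date". That footnote stands above the Table 4 heading.

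SAP 9.3 describes the appendix as "Rules for imputation of missing or partial dates to enable background calculation/classification of AEs and prior/concomitant medication/procedures". SAP 10.4 refers to Table 4 for prior or concomitant status.

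SAP 6.2.1 requires at least 3 days of systemic corticosteroids for an asthma exacerbation, derived by program from the Prior and Concomitant Medications page. Its footnote on asthma courses says that if use "is ongoing at the end of the study, the duration will be considered to be ≥ 3 days". It has no rule for a course that has ended but whose stop date is incomplete.

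**The concern.** A medication cannot end before it starts, yet three End Date rows of Table 4 can produce that result whenever the start falls after the last study dose. The adverse event table shows that the authors foresaw this problem, but the protection was not carried over to medications.

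Steroid courses are especially exposed. Protocol 8.7 has subjects who need systemic corticosteroids for asthma withdrawn from study drug, so the last dose will normally precede the steroid start, whichever of the three doses it was.

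At stake is one of the five components of the primary endpoint. Two programmers following the SAP could classify the same completed course differently: one applies Table 4 and finds an impossible duration, the other finds no rule and has to invent one. The choice carries into time to first asthma related event, which 6.2.1 dates from the start of the qualifying medication.

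**Working it through.** The plan states no figure for this rule, so the check applies the rows literally.

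**Inputs.** End Date rows: SAP Table 4. Threshold of 3 days and source page: SAP 6.2.1. Subjects per arm, 40: SAP 6.1.1. Last permitted dose Day 56 and final visit Day 98: protocol 10.1 and Table 1. Calendar dates and course lengths below are assumptions.

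**General result.** Let duration = end − start + 1. If the medication starts k days after the last dose (k ≥ 1) and the end is set to the last dose date, duration = −k + 1 = 1 − k. This is 0 for k = 1 and negative for every later start, so it never reaches 3.

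**Worked example (assumed dates).** Last dose 10 January; steroid 16 to 20 January.

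- True duration: 20 − 16 + 1 = 5 days. Criterion met.
- Day missing (same month), day and month missing (same year), or date fully missing: the end becomes 10 January. Duration 10 − 16 + 1 = −5 days. Criterion not met.
- End merely floored at the start date: 16 − 16 + 1 = 1 day. Still not met.
- Table 3 type fallback to the end of the start month: 31 − 16 + 1 = 16 days. Met.

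An order rule alone is therefore not enough; the fallback matters.

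**How often each row bites, given an incomplete date.** Every last-dose date in one assumed 365-day span was combined with every start from 1 day after the last dose, for courses of 3, 5, 7 and 10 days completed within 42 days of it (98 − 56 = 42). Share of courses with imputed duration under 3 days:

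| Missing part of end date | 3 days | 5 days | 7 days | 10 days |
|---|---|---|---|---|
| Day only | 32.0% | 29.1% | 26.1% | 21.8% |
| Day and month | 93.8% | 93.6% | 93.3% | 92.9% |
| Whole date | 100% | 100% | 100% | 100% |

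In every failing case the imputed end fell before the start. Where only the day is missing and the month differs from that of the last dose, the month-end row applies and these courses meet the criterion. The shares are conditional on the stop date being incomplete in that way; they do not estimate how many subjects are affected.

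**Effect of one subject.** 1/40 = 2.5 percentage points in that arm's event proportion, if no other criterion counts the subject.

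**Limit on any remedy.** Suppose a course starts on 30 January and the stop date is an unknown day in January. The longest possible duration is 31 − 30 + 1 = 2 days. A rule counting every incomplete stop date as at least 3 days would wrongly make this an event.

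**The case against.** The strongest reply is that Table 4 may never reach the endpoint. Section 10.4, the only analysis section that cites Table 4, uses it for prior or concomitant status. There the error is harmless: the last dose cannot precede the first, so the medication remains concomitant. Section 10.6.1 bases the primary endpoint on programmatic derivation from raw data, and 9.3 has listings show dates as collected. A reader might infer from Table 4 that such courses do fail the 3-day criterion. The documents do not establish that, and this part of the reply stands.

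It does not close the gap. The listings in 10.6 use the raw-data phrase to separate programmed events from Investigator-assessed ones; it does not address imputation. Section 9.3 covers calculation as well as classification, and Table 4 is the SAP's only rule for incomplete dates on the page that supplies the duration. If Table 4 is excluded, no rule remains.

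Other points limit the size, and they stand:

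- Not every incomplete end date goes to the last dose date; the month or year must match unless the whole date is missing.
- Some courses will be ongoing at the end of study, and 6.2.1 already counts those.
- The subject may qualify through SABA use, peak flow, or a hospital or emergency visit.
- The discordance listing in 10.6 could reveal a missed case if the Investigator recorded the event, and protocol 13.3.2 provides for consistency checks and queries. Neither changes the programmed result by rule.

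A reader might also take Days 57 to 98 as the period at risk. The trigger is each subject's own last dose, so courses after the Day 0 or Day 28 dose are exposed as well. Conversely, the same-month row affects only the rest of one calendar month. The length of that period does not measure exposure.

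**Conclusion.** The concern holds in conditional form. Table 4 lacks a rule that an end date may not precede the start date, and this is a defect whatever the table is used for. Section 6.2.1 does not say how steroid duration is judged when a completed course has an incomplete stop date. If Table 4 dates are used, a completed course begun after the subject's last dose gets a duration of zero or less, and fails the criterion, whenever the end is set to the last dose date.

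The size is probably small. The documents give no frequency of incomplete stop dates, and few cases are expected. Each subject lost from the composite moves an arm by 2.5 points, assuming 40 per arm and no other qualifying criterion. A lost placebo event narrows the treatment difference; a lost active-arm event widens it.

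The documents do not support saying that primary events will be dropped, or that every unknown end date is affected. They do support saying that a component of the primary endpoint is under-specified and that the only available rule can give an impossible date. That is worth correcting before unblinding.

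**What to change.** 1. **Table 4.** Add that an imputed end date may not precede the start date. If it would, use the earlier of the last day of the recorded month and the end-of-study date; if the month is unknown, use the end-of-study date.
2. **Section 6.2.1.** State that last-dose imputation from Table 4 does not determine steroid duration. A completed systemic corticosteroid course for asthma with an incomplete stop date counts as at least 3 days only when the recorded date parts allow 3 days or more. Flag each such case and have it confirmed through the sponsor confirmation that 6.2.1 already uses for unclear steroid cases, with that review explicitly blinded to treatment.

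The cost is a few SAP sentences and one programming check for end dates before start dates. No new data are needed.
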